8.5. Investigational Product Accountability and Disposal

The investigator, or designee, is responsible for taking an inventory of each shipment of IP received, and comparing it with the accompanying IP shipping order/packing list.

The investigator, or designee, will verify the accuracy of the information on the form, sign and date it, retain a copy in the study file, and return a copy to Celgene.

The IP will be stored according to the storage conditions identified on the drug label. At the study site, all IP will be stored in a locked, safe area to prevent unauthorized access.

Celgene (or designee) will review with the investigator and relevant site personnel the process for IP return, disposal, and/or destruction including responsibilities for the site versus Celgene (or designee).

8.6. Investigational Product Compliance

Study personnel will review the instructions printed on the package with the study subjects prior to dispensing the IP. Investigational Product will be dispensed as noted in [Table 4](#), Table of Events. The subjects will be instructed to return the IP containers, including any unused medication, to the study site at each visit for tablet counts and reconciliation. Subjects will be asked whether they have taken their IP as instructed at each study visit. Any problems with IP compliance will be reviewed with the subject. If a subject misses 4 or more consecutive days of dosing, Celgene must be contacted to decide whether dosing should resume or whether the subject should be terminated from the study, and enter into the Post-treatment Observational Follow-up Phase.

Gross compliance problems (eg, missing 4 or more consecutive days of dosing or taking less than 75% of the doses between study visits) should be discussed with Celgene. Compliance is defined as taking between 75% and 120% of dispensed IP.

8.6.1. Overdose

Overdose, as defined for this protocol, applies to protocol-required dosing of the IP (apremilast), and on a per dose basis, is defined as ingestion of greater than 100 mg of apremilast (greater than two AM or PM sections in the blister card) in any 24-hour dosing period whether by accident or intentionally. Adverse Events associated with an overdose must be collected on the AE page of the eCRF (see Section 11.1) for all overdosed subjects, but the overdose itself is not considered an AE. Other required or optional nonstudy drugs intended for prophylaxis of certain side effects, etc, are excluded from this definition.

For subjects receiving open-label apremilast 30 mg BID in the Extension Phase, overdose on a per dose basis is defined as ingestion of 4 or more 30-mg apremilast tablets in any 24-hour period whether by accident or intentional. On a schedule or frequency basis, overdose is defined as dosing more than 4 times in any 24-hour period.

Detailed information about any Celgene drug overdose in this study, regardless of whether the overdose was accidental or intentional, should be reported on the drug exposure eCRF page.

9. CONCOMITANT MEDICATIONS AND PROCEDURES

All medications (prescription and non-prescription), treatments, and therapies taken by the subject from screening throughout their entire participation in the study, including those initiated prior to the start of the study, must be recorded on the subject's source document and on the appropriate page of the eCRF. The dose, unit, frequency, route, indication, date the medication was started, and date the medication was stopped (if not ongoing) must be recorded.

9.1. Permitted Concomitant Medications and Procedures

The following medications are allowed during the study:

- Oral aminosalicylates (sulfasalazine [SSZ] or 5-ASA compounds) are allowed during the study, provided that treatment was initiated at least 6 weeks prior to screening, and has been given at a stable dose for at least 14 days prior to the Screening Visit. The dose of oral aminosalicylates must remain stable through the duration of the study or early termination from the study.
- Oral corticosteroids are allowed during the study, provided that the subject has been receiving therapy at a stable dose (prednisone \leq 20 mg/day or equivalent mg/day) for at least 3 weeks prior to the Screening Visit. The subject must remain on a stable dose until the Week 12 Visit, after which time the dose may be tapered according to the following tapering schedule:
 - For prednisone doses $>$ 10 mg (or equivalent) daily dose, each week the daily dose is to be tapered by 5 mg until a dose of 10 mg/day is reached, after that each week the daily dose is to be tapered by 2.5 mg until discontinuation.
 - For prednisone doses \leq 10 mg (or equivalent), each week the daily dose is to be tapered by 2.5 mg until discontinuation.
 - Subjects receiving budesonide should have their daily dose tapered by 3 mg every 3 weeks.
 - Subjects who experience UC-related symptoms after the tapering regimen is completed are permitted to receive the same corticosteroid treatment taken prior to the initiation of the tapering schedule, provided that the dosage is the same as the dose taken prior to tapering.

If oral corticosteroids were recently discontinued, discontinuation must have been completed at least 3 weeks prior to the Screening Visit.

- Acetaminophen and low-dose aspirin for cardiovascular prophylaxis are allowed.

Note: The dose of concomitant oral aminosalicylates cannot be increased above the baseline dose during the study. No new UC therapy can be prescribed once the subject has been randomized to the study.

9.2. Prohibited Concomitant Medications and Procedures

The following concomitant medications are prohibited during all treatment portions of the study including the Double-blind Placebo-controlled Phase (Week 0 to Week 12), the Blinded Active-treatment Phase (Week 12 to Week 52); and for subjects who participate in the Extension Phase, from Week 52 to Week 104, or to the Early Termination Visit for subjects who discontinue prematurely from the study:

- Use of the CYP3A4 inducers, rifampin and carbamazepine, bosentan, efavirenz, etravirine, modafinil, nafcillin, St. John's wort
- Uses of any biologic agents, including TNF blockers
- Use of mycophenolic acid, tacrolimus, sirolimus, cyclosporine or thalidomide
- Use of topical treatment with 5-ASA or corticosteroid enemas or suppositories is prohibited during the study and must be discontinued 2 weeks prior to the Screening Visit
- Use of intravenous corticosteroids is prohibited during the study and must be discontinued 2 weeks prior to the Screening Visit
- Use of AZA, 6-MP, or MTX is prohibited during the study and must be discontinued 8 weeks prior to the Screening Visit
- Chronic use of nonsteroidal anti-inflammatory drugs (NSAIDs).

9.3. Required Concomitant Medications and Procedures

There are no required concomitant medications.

Required procedures include endoscopy (rectosigmoidoscopy or colonoscopy) [REDACTED] as noted in Table 4. [REDACTED]

10. STATISTICAL ANALYSES

10.1. Overview

Key elements of the statistical analysis plan are outlined in this section. The comprehensive plan will be documented in a separate Statistical Analysis Plan (SAP).

Planned data analyses include: 1) an analysis at the completion of the 12-week Placebo-controlled Phase for all subjects (referred to as the Double-blind Placebo-controlled Phase analysis hereafter); 2) an analysis at the completion of the Active-treatment Phase for all subjects after 52 weeks of treatment; and 3) the final analysis at the completion of the entire study.

10.2. Study Population Definitions

Safety analyses will be based on the safety population, which will include all subjects who are randomized and receive at least one dose of IP. Subjects will be included in the treatment group corresponding to the IP they actually received for the analyses using the safety population.

The intent-to-treat (ITT) population will be the primary population for efficacy analyses. The ITT population will consist of all subjects who are randomized as specified in the protocol and receive at least one dose of IP. Subjects will be included in the treatment group to which they were randomized, irrespective of the treatment actually received, for the analyses using the ITT population.

The per-protocol (PP) population will consist of all subjects included in the ITT population who have at least one post-baseline efficacy evaluation and no protocol violations that may substantially affect the efficacy results. The final determination on these protocol violations, and thereby the composition of the PP population, will be made prior to the Placebo-controlled Phase analysis, and will be separately documented. Subjects will be included in the treatment group to which they were randomized, irrespective of the treatment actually received, for the analyses using the PP population.

10.3. Sample Size and Power Considerations

A 2-group chi-square test with a 0.1 two-sided significance level will have approximately 80% power to detect a true 20% absolute difference (30% versus 10%) between a dose of apremilast and placebo, for the proportion of subjects achieving a clinical remission at Week 12 when the sample size in each group is 49. Assuming a dropout rate of 10% prior to Week 12, approximately 165 subjects (approximately 55 subjects per group) are planned to be randomized in this study.

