Of note, available information from several compounds that are approved or were in development for IBD at the time of study start suggested that higher doses or more frequent dosing are required for the treatment of patients with IBD compared to patients with RA, PsA and/or psoriasis such as adalimumab (Humira[®]) (Humira, 2013), tofacitinib (Xeljanz[®])

(Sandborn, 2012, Xeljanz, 2012), and golimumab (Simponi®) (Simponi, 2013). Risk minimization measures such as ongoing safety review and Data Monitoring Committee (DMC) oversight were implemented to ensure that the safety of the subjects is adequately monitored.

The results from the first 12 weeks of this study indicated that subjects with active UC treated with apremilast 30 mg BID achieved meaningful improvements in symptoms of UC (remission), endoscopy, ^{CCI} [REDACTED] compared to placebo. Subjects treated with apremilast 40 mg BID achieved meaningful improvements in symptoms of UC (response) ^{CCI} [REDACTED] compared to placebo. An acceptable safety profile was observed in both the apremilast 30 mg and 40 mg BID dose groups. Based upon the similarity of the clinical, endoscopic ^{CCI} [REDACTED] endpoints in subjects treated with apremilast 30 mg and 40 mg BID and the plateau of dose response, as well as the extensive marketed safety experience with this dose, the 30 mg BID dose was determined to be the minimum dose that provides the maximum treatment response with an acceptable safety profile.

^{CCI} [REDACTED]

[REDACTED]

[REDACTED]

CCI

CCI

CCI

CCI

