10.6. Efficacy Analysis

The ITT population (Section 10.2) will be the primary population for efficacy analyses. A supportive analysis using the PP population will also be performed for the primary efficacy endpoint.

The comparisons for the primary efficacy endpoint will be based on two-sided statistical tests at a significance level of 0.1. A hierarchical approach will be used to adjust for multiplicity. For the primary endpoint, the first test in the hierarchy will be the apremilast 40 mg BID treatment group compared to placebo, followed by the apremilast 30 mg BID treatment group compared to placebo. If any of the active treatment groups (apremilast 30 mg or 40 mg BID) is discontinued prior to the end of the study, the treatment comparison will be conducted for the retained treatment group vs. placebo based on a two-sided statistical test at the 0.1 level. Additional endpoints subsequent to the primary endpoint comparisons may be added to the hierarchy and specified in the SAP.

Summary of all efficacy endpoints over time will be provided using frequency and percent for categorical endpoints and descriptive statistics for continuous endpoints.

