## 11. EFFICACY ANALYSIS

### 11.1. Multiplicity

Formal statistical tests, conducted at a 2-sided significance level of 0.1, are planned between APR 40 BID and placebo and between APR 30 BID and placebo for the primary efficacy endpoint. To control the family-wise Type 1 error rate at the 0.1 level, these 2 formal statistical tests will be carried out by using a fixed sequence testing procedure, with the comparison between APR 40 BID and placebo tested first. The comparison between APR 30 BID and placebo will be tested only if the comparison between APR 40 BID and placebo is statistically significant. If any of the 2 apremilast dose groups is discontinued prior to the end of the study, the treatment comparison will be conducted for the comparison between the retained apremilast dose and placebo at a 2-sided significance level of 0.1.

For formal statistical tests that are planned but not performed as a result of the aforementioned multiplicity adjustment strategy, as well as for any other comparisons that are not subjected to multiplicity adjustment, nominal 2-sided p-values (without adjustment for multiplicity) will be provided as a measure of the strength of association between the endpoint and the treatment effect rather than formal tests of hypotheses.

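### Does the 80% power statement mislead, given that 30 mg BID is formally tested only if 40 mg BID succeeds?

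*Protocol*

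**What the plan says.** Protocol 10.3 bases the sample size on "A 2-group chi-square test with a 0.1 two-sided significance level" and gives "approximately 80% power to detect a true 20% absolute difference (30% versus 10%) between a dose of apremilast and placebo" "when the sample size in each group is 49". It allows for 10% dropout before Week 12 and arrives at about 55 per group, 165 in all. SAP 4.4 repeats this.

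The testing order is given elsewhere. Protocol 10.6 says that "the first test in the hierarchy will be the apremilast 40 mg BID treatment group compared to placebo", with 30 mg BID second. SAP 11.1 spells out the gate: "The comparison between APR 30 BID and placebo will be tested only if the comparison between APR 40 BID and placebo is statistically significant". If the gate closes, SAP 11.1 says that "nominal 2-sided p-values (without adjustment for multiplicity) will be provided as a measure of the strength of association". Both sections add one exception: if a dose arm is dropped, the retained dose is compared with placebo directly at the 0.1 level.

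Protocol 10.6.1 and SAP 11.3.1 specify a stratified Cochran-Mantel-Haenszel (CMH) test for the primary endpoint. Subjects who discontinue before Week 12 count as nonresponders.

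**The concern.** The primary objective names both doses, and the power section speaks of an unspecified dose of apremilast. A quick reader could conclude that each dose has an 80% chance of a formal positive result. Under the fixed sequence that is true only of 40 mg BID. The 30 mg BID claim needs two successes against a shared placebo arm, so its power cannot exceed that of the 40 mg BID test, and it falls below 80% unless 40 mg BID is clearly the more effective dose.

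What would be at stake is how a 30 mg BID result is read. In some trials 30 mg BID would pass its own 0.1 test and still receive only a nominal p-value because 40 mg BID missed. Someone who believed the design gave 30 mg BID an 80% chance of a formal claim would misjudge how likely that outcome was.

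**Working it through.** **Inputs.** Placebo remission 10%, apremilast 30%, two-sided level 0.1, 49 per group, 10% dropout, 55 per group randomized (Protocol 10.3, SAP 4.4). Fixed sequence with 40 mg BID first (Protocol 10.6, SAP 11.1). Dropouts count as nonresponders (Protocol 10.6.1). The documents do not say that both doses have 30% remission; that is an assumption.

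**The plan's own figures.** The mean rate is (0.30 + 0.10)/2 = 0.20.

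- n = [1.645 × √(2 × 0.20 × 0.80) + 0.8416 × √(0.21 + 0.09)]² / 0.20² = [0.9306 + 0.4610]² / 0.04 = 48.4, so 49.
- Power at 49: Φ[(0.20 × √49 − 0.9306)/0.5477] = Φ(0.857) = 80.4%. Exact binomial enumeration of the uncorrected chi-square test gives 81.4%.
- Dropout: 49/0.9 = 54.4, so 55; 3 × 55 = 165.

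All of these match the documents.

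**Power for a formal 30 mg BID claim.** This is the probability that both tests succeed. The shared placebo arm correlates the two test statistics: 0.09/(0.09 + 0.21) = 0.30. A bivariate normal with that correlation gives the normal figures below. The exact figures enumerate three binomial arms with uncorrected chi-square tests. Both doses have the same rate in every row.

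| Setting | One test, normal / exact | Both tests, normal / exact | 30 mg BID passes its own test but is gated out |
|---|---|---|---|
| 49 per group, 30% v 10% | 80.4% / 81.4% | 67.3% / 70.2% | 13% / 11% |
| 55 per group, 27% v 9% | 79.8% / 80.8% | 66.3% / 69.6% | 14% / 11% |
| 55 per group, 30% v 10% | 84.4% / 85.1% | 73.2% / 75.7% | 11% / 9% |

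The last column is one-test power minus both-test power. The second row treats 30% and 10% as rates among completers and counts the 10% dropouts as nonresponders (0.9 × 30% = 27%, 0.9 × 10% = 9%). The third row treats 30% and 10% as rates that already include dropouts as nonresponders. Protocol 10.3 does not say which is meant.

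The stratified CMH test gives much the same answer. Simulation with 100,000 runs, an assumed 40% prevalence for each stratification factor and equal rates across strata gave a both-test power of 69.1% at 49 per group. At 55 per group it was 68.7% (27% v 9%) and 74.6% (30% v 10%).

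**If the doses differ.** With 30 mg BID at 30%, 49 per group and assumed 40 mg BID rates that are not in the documents, the power for a formal 30 mg BID claim is:

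- 40 mg BID at 20%: 35-37%
- 40 mg BID at 25%: 54-56%
- 40 mg BID at 35%: 75-78%
- 40 mg BID at 40%: 79-80%

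These show the direction only.

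**What the gate buys.** Splitting the level equally, 0.05 per dose, would give each dose Φ[(1.4 − 1.96 × 0.5657)/0.5477] = Φ(0.532) = 70.3% at 49 per group. On the same normal approximation, the fixed sequence gives 80.4% for 40 mg BID and 67.3% for 30 mg BID. It costs 30 mg BID 3.0 percentage points and saves 40 mg BID 10.1, if the doses are equally effective.

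**The case for a change.** The strongest case for a change is that a plan which adopts a hierarchy should report power that reflects it. The objective covers both doses, and SAP 11.3.1 sets out to test each. With both doses at 30% and 49 per group, the chance of missing a formal 30 mg BID claim is 30-33%, not about 20%. A change of wording in two sections would say so, at no cost in patients.

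The arithmetic stands, and so does the observation that neither document reports this figure. The claim that the power section misstates anything does not stand. It names a two-group test and one dose against placebo, which is per-comparison wording, and nothing extends the 80% to the second test or to both.

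It is also too strong to say that a reader needs the joint power to interpret a gated-out 30 mg BID result. SAP 11.1 already labels such a p-value nominal, and SAP 11.3.1 supplies treatment differences with 95% confidence intervals. Planned power does not change what an observed estimate and interval show.

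Protocol 1.4.3 describes the Week 12 findings in terms of remission for 30 mg BID and response for 40 mg BID. That passage is qualitative and partly redacted, and it does not say whether the 40 mg BID test was significant. It does not show whether the gate closed.

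**Conclusion.** No change is needed. The stated 80%, 49, 55 and 165 are all correct for what they describe, and 80% is the right figure for the first test in the sequence. The power for a formal 30 mg BID claim is lower: 67-70% at 49 per group, and 66-70% or 73-76% at 55 per group depending on whether the assumed rates already include dropouts. These figures rest on equal 30% remission on both doses and on both arms being retained.

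Sizing a Phase 2 trial per comparison is a legitimate choice. The plan sets no target for joint power, and the gate, its exception and the status of a gated-out result are all stated. Protocol 4.1.3 records that all subjects have completed the 12-week phase, and Protocol 1.4.3 describes the results. Sample size, order and level are therefore fixed, and a revised design-stage power sentence would alter no analysis and no conclusion. Anyone who wants the joint power for context can derive it from the stated inputs, as above.

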10.4. Background and Demographic Characteristics

Subjects' age, height, weight, and other continuous demographic and baseline characteristics will be summarized using descriptive statistics, while gender, race and other categorical variables will be provided using frequency tabulations. Medical history data will be summarized using frequency tabulations by system organ class and preferred term.

10.5. Subject Disposition

Subject disposition (analysis population allocation, entered, discontinued along with primary reason for discontinuation, completed) will be summarized using frequency and percent for both treatment and follow-up phases. A summary of subjects enrolled by site will be provided. Protocol violations/deviations will be summarized using frequency tabulations.

10.6. Efficacy Analysis

The ITT population (Section 10.2) will be the primary population for efficacy analyses. A supportive analysis using the PP population will also be performed for the primary efficacy endpoint.

The comparisons for the primary efficacy endpoint will be based on two-sided statistical tests at a significance level of 0.1. A hierarchical approach will be used to adjust for multiplicity. For the primary endpoint, the first test in the hierarchy will be the apremilast 40 mg BID treatment group compared to placebo, followed by the apremilast 30 mg BID treatment group compared to placebo. If any of the active treatment groups (apremilast 30 mg or 40 mg BID) is discontinued prior to the end of the study, the treatment comparison will be conducted for the retained treatment group vs. placebo based on a two-sided statistical test at the 0.1 level. Additional endpoints subsequent to the primary endpoint comparisons may be added to the hierarchy and specified in the SAP.

Summary of all efficacy endpoints over time will be provided using frequency and percent for categorical endpoints and descriptive statistics for continuous endpoints.

10.6.1. Primary Efficacy Endpoint

The primary efficacy endpoint is clinical remission, as defined as a TMS of ≤ 2 with no individual subscore > 1 at Week 12. The proportion of subjects who achieve a clinical remission at Week 12 between any apremilast (30 mg BID or 40 mg BID) group and the placebo group will be compared using the Cochran-Mantel-Haenszel (CMH) test controlling for the randomization stratification factors specified. Subjects who prematurely discontinue the study before Week 12 will be considered as nonresponders.

10.6.2. Secondary Efficacy Endpoints

The secondary efficacy endpoints defined in Section 3.2.1 will be analyzed using the CMH test controlling for the randomization stratification factors as will be done for the primary efficacy endpoint.

CCI

CCI [REDACTED]

[REDACTED] [REDACTED]

[REDACTED]

10.7. Safety Analysis

The safety analyses will be performed using the safety population (Section 10.2).

Treatment-emergent adverse events will be classified using the Medical Dictionary for Regulatory Activities (MedDRA) classification system. All AEs will be summarized by system organ class, preferred term, severity and relationship to IP. Adverse events leading to death or to discontinuation from treatment and SAEs will also be tabulated. In the by-subject analysis, a subject having the same event more than once will be counted only once and by greatest severity.

Laboratory data will be summarized descriptively by visit. In addition, shift tables showing the number of subjects with values low, normal, and high compared to the normal ranges pretreatment versus post-treatment will be provided.

Vital sign measurements, including weight, will be summarized descriptively by visit.

CCI [REDACTED]

[REDACTED]

[REDACTED]

[REDACTED] [REDACTED]

[REDACTED]

